1.0 Objectives

1.1 Study Objectives

Describe the purpose, specific aims or objectives. State the hypotheses to be tested.

The purpose of the proposed study is to examine how replacement of habitually consumed snack foods in the U.S. with 2 oz./day of pecans affects markers of peripheral vascular health, lipids and lipoproteins, blood pressure, and glycemic control compared to usual U.S. intake.

The aims of the study are as follows:

- 1) To evaluate whether consuming 2 oz/day of pecans as a snack improves flow mediated dilation compared with habitual intake in individuals at elevated risk for cardiovascular disease;
- 2) To assess changes in pulse wave velocity, lipids and lipoproteins (concentration, particle size and number), blood pressure (central and peripheral) and glycemic control in each group.

Hypothesis:

It is hypothesized that replacement of typical snack foods with 2 oz./day of pecans will improve peripheral vascular assessments, lipid and lipoprotein profile and glycemic control compared to habitual average American intake.

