8.3 Statistical methods

Describe the statistical methods (or non-statistical methods of analysis) that will be employed.

The normality of the data will be tested before performing analyses, and transformations will be made if needed. In the primary analyses, the change in outcome measures (baseline to 12 weeks) will be compared between groups after adjustment for baseline value, age, sex, and BMI. The mixed model

procedure will be used (SAS) with randomization as a fixed factor, and baseline value for the outcome measure, age, sex, and BMI included as covariates.

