Cardiometabolic Effects of Pecans as a Snack

NCT05071807

September 19, 2023

The sample size calculation was based on FMD, the primary outcome. To detect a 1.2 percentage point (standard deviation 2.4; effect size 0.5) between-group difference in the change in FMD with 80% power ($\alpha=0.05$), it was estimated that a sample size of 128 participants was needed (64 per group) (40-43).

All analyses were performed in SAS (version 9.4; SAS Institute Inc.). All data collected from randomly assigned participants were included in data analyses consistent with intent-to-treat principles. All residuals for regression models were checked for normality via normal probability (Q-Q) plots. When the residuals were non-normally distributed, log transformation was conducted, which improved the residual distribution to approximately normal. Linearity was investigated by plotting model residuals against the outcome of interest and for all variables the assumption of linearity was met. All models were adjusted for outcome baseline value, age (years), sex (male or female) and baseline BMI (kg/m²). For all described tests, effect modification by sex was examined by evaluating the group by sex interaction. If the group by sex interaction main effect was not significant it was excluded from the final model. The primary analyses for the vascular and cardiometabolic outcomes assessed between group (pecan or usual diet) differences in the change from baseline. The change from baseline was calculated by subtracting the endpoint value from the baseline value. Weight, lipids/lipoproteins, glucose and insulin were measured on two test days at each time point and values were averaged for analysis to improve measurement precision. Between-group differences in the change from baseline for all vascular and cardiometabolic outcomes were assessed using linear regression models.

For diet quality, linear mixed models were used to account for the repeated nature of the outcome. Group was included as a fixed effect and time point was included as a repeated effect. Intervention effects were determined by examining the group by visit interaction. When a significant group by time point interaction was detected, post hoc testing was conducted and the Tukey-Kramer method was used to adjust for multiple comparisons. Statistical significance was set at $p < 0.05$.

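### The SAP lets a group-by-sex test decide whether the primary FMD model keeps an interaction term; protocol 8.3 has no such step, and no overall contrast is named if the term stays (minor)

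*SAP*

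**What the plan says.** The SAP applies the check to everything: "For all described tests, effect modification by sex was examined by evaluating the group by sex interaction". FMD is the primary outcome, so it is covered. The stated rule for the term is "If the group by sex interaction main effect was not significant it was excluded from the final model". The only significance level given is "Statistical significance was set at $p < 0.05".

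The SAP describes the main comparison thus: "The primary analyses for the vascular and cardiometabolic outcomes assessed between group (pecan or usual diet) differences in the change from baseline". It gives no sex weights and no contrast for a model that contains group by sex. Its only follow-up rule for a significant interaction is in the diet-quality paragraph and concerns a different term: "When a significant group by time point interaction was detected, post hoc testing was conducted".

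Protocol section 8.3 sets the primary model "with randomization as a fixed factor, and baseline value for the outcome measure, age, sex, and BMI included as covariates". It lists no interaction and no selection step. The SAP uses the same adjustment set, so the two documents differ only in the group-by-sex step.

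Aim 1 in protocol section 1.1 asks whether "consuming 2 oz/day of pecans as a snack improves flow mediated dilation compared with habitual intake in individuals at elevated risk for cardiovascular disease", which is one overall comparison. The SAP's sample size is likewise set "To detect a 1.2 percentage point (standard deviation 2.4; effect size 0.5) between-group difference in the change in FMD with 80% power".

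**The concern.** Examining effect modification by sex does not conflict with the protocol. Letting the p-value of that check decide which model supplies the primary result does depart from section 8.3.

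Once group by sex is in the model, there is no longer a single group effect. The figure reported could be an average with equal sex weights, an average weighted by the observed share of each sex, or the coefficient for one reference sex. These differ whenever the estimated effects differ between the sexes, which is the situation in which the term is kept. The reported FMD effect then need not be the overall difference in aim 1 and the sample size. If the term is dropped, the final model has exactly the protocol 8.3 covariates and nothing changes.

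**Working it through.** **Inputs.** From the documents: 64 per group, design difference 1.2 percentage points (pp), SD 2.4, alpha 0.05, power 80%; covariates baseline value, age, sex, BMI. Assumed, because the documents do not give them: 50 to 70% women, the same share in both arms; residual SD equal to the design SD of 2.4 (1.8 also shown, in case covariate adjustment lowers it); the interaction tested at two-sided 0.05.

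**The plan's own figure.** n per arm = 2 × (1.960 + 0.842)² × (2.4/1.2)² = 62.8, so 63 by the normal formula. With the noncentral t, 63 per arm gives 79.5% power and 64 gives 80.1%. The stated 64 per arm is reproduced, for a single two-sided between-group difference.

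**What each contrast estimates.** Let p be the share of women and d the difference between the effect in women and the effect in men. The model without the interaction estimates, very nearly, the average weighted by the observed shares. Relative to that:
- male-reference coefficient: off by p × d
- female-reference coefficient: off by (1 − p) × d
- equal-weight average: off by |p − 0.5| × d
- observed-share average: no shift

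**Size when the interaction just reaches p = 0.05.** SE of the interaction = SD × √[(2/64) × (1/p + 1/(1 − p))]. The model has 7 coefficients, so df = 128 − 7 = 121 and the t value is 1.98.

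| | p = 0.5 | p = 0.6 | p = 0.7 |
|---|---|---|---|
| SE, SD 2.4 (pp) | 0.849 | 0.866 | 0.926 |
| Smallest significant d (pp) | 1.68 | 1.71 | 1.83 |
| Equal-weight shift (pp) | 0 | 0.17 | 0.37 |
| Male-reference shift (pp) | 0.84 | 1.03 | 1.28 |
| Female-reference shift (pp) | 0.84 | 0.69 | 0.55 |

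Example at p = 0.7: 0.2 × 1.83 = 0.37 and 0.7 × 1.83 = 1.28. With SD 1.8 every entry falls by a quarter: equal weight 0 to 0.27 pp, one-sex 0.41 to 0.96 pp.

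**False-positive rate of the two-step rule.** 100,000 simulated trials per scenario with no group effect and no interaction, 64 per arm, SD 2.4, full covariate model; Monte Carlo SE about 0.07 point.

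| | p = 0.5 | p = 0.6 | p = 0.7 |
|---|---|---|---|
| Term kept | 5.0% | 5.1% | 5.0% |
| Fixed protocol 8.3 model | 4.9% | 5.1% | 5.0% |
| Two-step, observed-share average | 4.9% | 5.1% | 5.0% |
| Two-step, equal-weight average | 4.9% | 5.3% | 5.4% |
| Two-step, male reference | 6.4% | 7.0% | 7.1% |
| Two-step, female reference | 6.3% | 6.3% | 5.8% |
| Median shift if kept, equal weight (pp) | 0.06 | 0.20 | 0.44 |
| Median shift if kept, observed share (pp) | 0.01 | 0.01 | 0.01 |

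Two further simulations agree. One, with known SD and 400,000 runs at p = 0.5 and 0.7, gave 5.0% and 5.4% for equal weights and 5.8 to 7.2% for one sex. The other, with 40,000 runs per scenario, gave 5.2 to 5.5% and 5.6 to 7.1%, with the same median shifts. Taken together: about 5.0 to 5.5% for the equal-weight average and 5.6 to 7.2% for a one-sex coefficient.

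**Why the overall rate barely moves.** At p = 0.7 the equal-weight average rejects in 13.8% of the trials that keep the term. These are about 5% of all trials, so overall 0.95 × 5.0% + 0.05 × 13.8% = 5.4%.

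**The case against.** The strongest reply is that nothing of substance follows. The SAP speaks of between-group differences, which points to an average over the sexes. On that reading the overall error rate stays within about half a point of 5%. Averaged over all null trials, the equal-weight estimate differs from the fixed-model estimate by only 0.00, 0.01 and 0.02 pp at 50, 60 and 70% women. This stands, and it is why the point is minor.

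Retention is also an inference. The SAP states only when the term is excluded, and the 0.05 level for this test is taken from its general significance statement. This stands too. A reader might infer that a sex interaction was found and altered the FMD result, but neither document says that any term was significant or kept.

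The simulations cover only the case of no true interaction. If the effect really differs by sex, an overall figure alone could mislead, and keeping the term is a defensible modelling choice. This stands in part. It is a reason to show sex-specific estimates, not a reason for the primary estimate to change its meaning according to a test.

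Finally, the SAP is written in the past tense, so rewording it cannot pre-specify anything. That is fair. What remains useful is a clear statement of which model gave the primary result.

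**Conclusion.** The point holds as a minor one. The final primary model depends on a test that protocol 8.3 does not contain, and the SAP names no overall contrast for the case where the term stays. With no true interaction that case arises in about 5% of trials. With an equal-weight average the overall false-positive rate is about 5.0 to 5.5%, against 5% for the fixed model, and the median shift in trials that keep the term is 0.06 to 0.44 pp against the 1.2 pp design difference. These figures rest on an assumed 50 to 70% women, SD 2.4 and a 0.05 threshold for the interaction. The sample size of 128 is unaffected.

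Two stronger readings are not supported. The first is that a single reference-sex coefficient would be reported as the overall pecan effect. That would raise the overall rate to about 5.6 to 7.2% and give threshold shifts of 0.55 to 1.28 pp (SD 2.4), but neither document says it would be done, and the SAP's between-group wording points the other way. The second is to read the rates among only the trials that keep the term (5.9 to 13.8% for equal weights, 22 to 48% for one sex) as the error rate of the procedure. They condition on an event that occurs in about 1 null trial in 20.

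**What to change.** Take the primary FMD effect, and that of the other vascular and cardiometabolic linear regressions, from the protocol 8.3 covariate set (group, baseline value, age, sex, baseline BMI) whatever the group-by-sex p-value. Report the interaction with its 95% CI and the sex-specific estimates separately, labelled exploratory.

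State whether any group-by-sex term was kept. If one was, re-run that outcome without it, or give the group difference weighted by the observed share of each sex, which reproduced the fixed model in the simulation.

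The diet-quality mixed model can stay as it is, because its intervention effect is defined as the group-by-visit interaction and not as a single group coefficient.

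Cost: wording only if no term was kept, otherwise one re-run per affected outcome; no new data. The downside is that a real sex difference would be reported as an exploratory finding.
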